7.4.5.3. Pregnancy Testing

Pregnancy testing will be performed on all female subjects as noted in the schedules of assessments in **Table 1**. Serum pregnancy test will be obtained at screening. A urine pregnancy test will be obtained all other visits. A positive urine pregnancy test should be confirmed by a serum pregnancy test.

7.5. Efficacy Assessments

7.5.1. Numerical Rating Scale (NRS) Itch Score

The Pruritus NRS is a patient reported measure of itch intensity assessed using an 11-point scale (0 = no itch to 10 = worst imaginable itch). NRS itch scores will be measured at baseline and at every visit to monitor improvement. Furthermore, NRS scores will be obtained for the prior 24 hours, and the week prior in sequential order.

7.5.1.1. Worsening of CIP

If worsening of CIP is present, then NRS scores will be noted.

7.5.2. Dermatology Life Quality Index (DLQI)

The Dermatology Life Quality Index or DLQI, developed in 1994, was the first dermatology-specific Quality of Life (QOL) instrument. It is a simple 10-question validated questionnaire that has been used in over 40 different skin conditions in over 80 countries and is available in over 90 languages. Its use has been described in over 1000 publications including many multinational studies. The DLQI is the most frequently used instrument in studies of randomised controlled trials in dermatology. The DLQI 10-question validated questionnaire to measure quality of life impact and will be measured at Baseline and at every visit (see Appendix B).

7.6. Skin Biopsy Analysis: RNA Seq Analysis and Histology

Skin biopsy analysis will be used to investigate molecular signatures associated with response or resistance to treatment with the study drug. Ribonucleic acid (RNA) will be extracted from these samples to perform RNA-seq analysis that may include genome-wide gene expression profiling. The tissue will also be examined histopathologically.

8. SAFETY MONITORING AND REPORTING

8.1. Adverse Events

8.1.1. Definitions Adverse Events and Serious Adverse Events

An adverse event (AE) is any noxious, unintended, or untoward medical occurrence occurring at any dose that may appear or worsen in a subject during the course of a study. It may be a new intercurrent illness, a worsening concomitant illness, an injury, or any concomitant impairment of the subject's health, including laboratory test values (as specified by the criteria below), regardless of etiology. Any medical condition that was present prior to study treatment and that remains unchanged or improved should not be recorded as an AE. If there is a worsening of that medical condition this should be considered an AE. A diagnosis or syndrome should be recorded on the AE page of the Case Report Form rather than the individual signs or symptoms of the diagnosis or syndrome.

All AEs will be recorded by the Investigator(s) from the time of signing the informed consent through the end of the designated follow-up period.

Abnormal laboratory values defined as adverse events

An abnormal laboratory value is considered to be an AE if the laboratory abnormality is characterized by any of the following:

- Results in discontinuation from the study.

- Requires treatment, modification/interruption of study drug dose, or any other therapeutic intervention.
- Is judged by the Investigator(s) to be of significant clinical importance.

If a laboratory abnormality is one component of a diagnosis or syndrome, then only the diagnosis or syndrome should be recorded on the AE page of the CRF. If the abnormality was not a part of a diagnosis or syndrome, then the laboratory abnormality should be recorded as the AE.

Serious adverse event

A serious adverse event (SAE) is any AE which:

- Results in death
- Is life-threatening (i.e., in the opinion of the Investigator(s) the subject is at immediate risk of death from the AE)
- Requires inpatient hospitalization or prolongation of existing hospitalization
- Results in persistent or significant disability/incapacity (a substantial disruption of the subject's ability to conduct normal life functions)
- Results in a congenital anomaly/birth defect
- Constitutes an important medical event

Important medical events are defined as those occurrences that may not be immediately life threatening or result in death, hospitalization, or disability, but may jeopardize the subject or require medical or surgical intervention to prevent one of the other outcomes listed above.

Medical and scientific judgment should be exercised in deciding whether such an AE should be considered serious.

Events not considered to be SAEs are hospitalizations which: were planned before entry into the clinical study; are for elective treatment of a condition unrelated to the studied indication or its treatment; occur on an emergency outpatient basis and do not result in admission (unless fulfilling other criteria above); are part of the normal treatment or monitoring of the studied indication and are not associated with any deterioration in condition.

If an AE is considered serious, both the AE pages of the CRF and the SAE Report Form must be completed.

For each SAE, the Investigator(s) will provide information on severity, start and stop dates, relationship to study drug, action taken regarding study drug, and outcome.

Classification of severity

For both AEs and SAEs, the investigator(s) must assess the severity of the event. The AEs will be evaluated for severity according to the following scale:

Grade 1 = Mild

Grade 2 = Moderate

Grade 3 = Severe

Classification of Relationship/Causality of adverse events (SAE/AE) to study drug

The Investigator(s) must determine the relationship between the administration of study drug and the occurrence of an AE/SAE as Not Suspected or Suspected as defined below:

Not suspected: The temporal relationship of the adverse event to study drug administration makes a causal relationship unlikely or remote, or other medications, therapeutic interventions, or underlying conditions provide a sufficient explanation for the observed event

Suspected: The temporal relationship of the adverse event to study drug administration makes a causal relationship possible, and other medications, therapeutic interventions, or underlying conditions do not provide a sufficient explanation for the observed event

8.2. Reporting Serious Adverse Events: Immediate

Any AE that meets the any criterion for a SAE requires the completion of an SAE Report Form in addition to being recorded on the AE pages of the CRF. The Investigator(s) is required to ensure that the data on these forms is accurate and consistent. This applies to all SAEs, regardless of relationship to study drug, that occur during the study, those made known to the Investigator(s) within 30 days after a subject's last dose of study drug, and those made known to the investigator(s) at anytime that are suspected of being related to study drug. The SAE must be reported immediately (i.e., within 24 hours of the Investigators' knowledge of the event) to Celgene Safety by facsimile. A written report (prepared by the Investigator(s) using an SAE Report Form or a 3500A Medwatch form is to be faxed to Celgene Drug Safety.

Celgene Drug Safety Contact Information:

Celgene Corporation, Global Drug Safety and Management
[name]

[contact]

EMAIL [contact]

The SAE report should provide a detailed description of the SAE. If a subject has died and an autopsy has been performed, copies of the autopsy report and death certificate are to be sent to Celgene as soon as these become available. Any follow-up data will be detailed in a subsequent SAE Report Form or Medwatch form and sent to Celgene.

The Investigator(s) is responsible for informing the Institutional Review Board/Ethics Committee (IRB/IEC) of the SAE and providing them with all relevant initial and follow-up information about the event. The Investigator(s) must keep copies of all

SAE information, including correspondence with Celgene and the IRB/IEC, on file. All SAEs that have not resolved upon discontinuation of the subject's participation in the study must be followed until either the event resolves completely, stabilizes/resolves with sequelae, or returns to baseline (if a baseline value is available).

8.3. Pregnancy

Pregnancies and suspected pregnancies (including a positive pregnancy test regardless of age or disease state) of a female subject or the female partner of a male subject occurring while the subject is on study drug, or within 30 days of the subject's last dose of study drug, are considered immediately reportable events. Study drug is to be discontinued immediately and the subject instructed to return any unused portion of the study drug to the investigator(s). The pregnancy, suspected pregnancy, or positive pregnancy test must be reported to Celgene Safety immediately facsimile using the Pregnancy Report form provided by Celgene.

The female should be referred to an obstetrician-gynecologist experienced in reproductive toxicity for further evaluation and counseling.

The Investigator(s) will follow the female subject until completion of the pregnancy, and must notify Celgene Safety of the outcome of the pregnancy as a follow-up on the follow up Pregnancy Reporting form.

If the outcome of the pregnancy meets the criteria for immediate classification as a SAE (i.e., spontaneous or therapeutic abortion [any congenital anomaly detected in an aborted fetus is to be documented], stillbirth, neonatal death, or congenital anomaly [including that in an aborted fetus]), the Investigator(s) should follow the procedures for reporting SAEs (i.e., report the event to Celgene Safety by facsimile within 24 hours of the Investigator's knowledge of the event).

In the case of a live "normal" birth, Celgene Safety should be advised by facsimile within 24 hours of the Investigator's knowledge of the event.

All neonatal deaths that occur within 30 days of birth should be reported, without regard to causality, as SAEs. In addition, any infant death after 30 days that the Investigator(s) suspects is related to the in utero exposure to the study drug should also be reported to Celgene Safety by facsimile within 24 hours of the Investigators' knowledge of the event.

If the female is found not to be pregnant, any determination regarding the subject's continued participation in the study will be determined by the Investigator.

8.4. Overdose

Abuse, withdrawal, sensitivity, or toxicity to an investigational product should be reported as an AE. Overdose, accidental or intentional, whether or not it is associated

with an AE should be reported as an AE. Any sequela of an accidental or intentional overdose of an investigational product should be reported as an AE.

If the sequela of an overdose is an SAE, then the sequela must be reported on an SAE report form. The overdose resulting in the SAE should be identified as the cause of the event on the SAE report form but should not be reported as an SAE itself.

In the event of an overdose, the subject should be monitored as appropriate and should receive supportive measures as necessary. There is no known specific antidote for apremilast overdose. Actual treatment should depend on the severity of the clinical situation and the judgment and experience of the treating physician.

Overdose for this protocol, on a per dose basis, is defined as ingestion of any more than the amount prescribed of apremilast (or matching placebo) tablets in any 24 hour period whether by accident or intentionally.

8.5. Data Monitoring Committee

No external data monitoring committee will be used, however, safety data will be monitored throughout the study directly by the investigator and the study team.

8.6. Product Complaints

The investigator is responsible for reporting a complete description of the product complaint via email or other written communication to Celgene as noted in the packaging information. Any AE associated with a product complaint should be reported as described in Section 8.2 of this Protocol.

9. STATISTICS

9.1. Study Populations

The intent-to-treat (ITT) population includes all subjects enrolled into the trial.

The per protocol (PP) population includes all subjects who are considered to be sufficiently compliant with the Protocol.

The safety evaluable population includes all subjects who applied at least 1 dose of study drug. Treatment groups for this population will be determined according to the actual treatment the subject received on Day 0.

9.2. Selection of Sample Size

The same patient will be compared at two time points therefore we will perform a paired t-test analysis of the NRS itch score. However, we will also have additional visits in between the two time points therefore we will have additional data points that can be further incorporated for more extensive statistical analyses. All patients will start at a high NRS score of 7 or greater there will be very little variability in the initial study population. Based on a random sampling of 10 patients with CIP in our clinic with histopathologic findings of dermal edema, eosinophil infiltration, mast cell activation and/or lymphocytic infiltration, we identified a mean NRS score of 8.8 with a standard deviation of 1.1. The NRS scale runs from 0 to 10 thus any significant decrease in our NRS score will be captured with even a small sample size. N = 10 should be more than sufficient based on this amount of variance and starting NRS score.

9.3. Level of Significance

We aim to reach statistical significance with our current design of a *P*-value of 0.05 or lower. If we do not, but observe a strong trend, we will perform power calculations to determine what level of enrollment would require the detection of a statistically significant effect.

9.4. Statistical Analyses

9.4.1. Efficacy Analyses

9.4.1.1. Efficacy Measures for Primary and Secondary Endpoints

9.4.1.1.1 Numerical Rating Scale (NRS) itch score

Numerical Rating Scale (NRS) itch score is a single-question assessment tool with a scale of 0-10, with 0 being 'no itch' and 10 'worst itch imaginable'. The average NRS itch score will be measured overall, for the prior 24 hours first and then the prior one week. The NRS itch score improvement will be calculated relative to baseline at each visit. The primary endpoint is the change from baseline in NRS at Week 12.

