
Primary Objectives:
 
 To demonstrate that apremilast 30 mg taken twice daily (BID) results in improvement in Numerical Rating Scale (NRS) itch score from Baseline. 
Secondary Objective:
 
Key Secondary objectives:
 
 To demonstrate that apremilast 30 mg taken twice daily (BID) results in improvement in Dermatology Life Quality Index (DLQI) from Baseline. 
Exploratory Objectives:
 
 To identify whether skin transcriptomic signatures are altered in response to treatment with apremilast by RNA-seq analysis. 	

Primary Endpoints:
 
 Absolute change from Baseline in Numerical Rating Scale (NRS) itch score to week 16. The NRS itch score will be recalled from the prior 24 hours first and then the prior 1 week. 
Secondary Endpoints:
 
Key secondary endpoints:
 
 Absolute change from Baseline in Dermatology Life Quality Index (DLQI) to week 16. 
Other secondary endpoints:
 
 NRS itch score at Screening, Baseline, Weeks 2, 4, 8, 12 and 16, and 18. Dermatology Life Quality Index (DLQI) at Screening, Baseline, Weeks 2, 4, 8, 12, 16, and 18. AEs; performing physical examinations; collecting vital signs; and collecting laboratory data for hematology and serum chemistry. 
Exploratory Endpoints:
 
 Skin RNA-seq analysis at Week 0 and Week 16. 	

Overall Study Design:
 
This study is an open label pilot study to test the efficacy of apremilast in the treatment of chronic idiopathic pruritus (CIP). Ten subjects who meet the eligibility criteria will be enrolled. The total duration of subject participation will be seven study visits over approximately 22 weeks. All subjects will receive apremilast 30 mg by mouth BID for 16 weeks. Subjects will have follow-up assessments 2 weeks after the last dose.
	

Study Population: Men or women, aged ≥ 18 years, who have been diagnosed with CIP with a NRS itch score of ≥ 7 .

Key Inclusion Criteria: A subject who meets all of the following criteria may be included in the study:

- Male and non-pregnant, non-lactating female subjects aged 18 years or older
- Diagnosed with chronic idiopathic pruritus (CIP) with an NRS Itch Score of ≥ 7 at both Screening and Baseline
- Diagnosis of CIP for at least 6 weeks prior to screening

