2.2. Study Endpoints

2.2.1. Primary Endpoint

- Absolute change in Numerical Rating Scale (NRS) itch score from Baseline to Week 16. The NRS itch score will be recalled from the prior 24 hours first and then the prior 1 week.

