2.2.2. Secondary Endpoint(s)

Key secondary endpoints:

- Absolute change in Dermatology Life Quality Index (DLQI) from Baseline to week 16.

Other secondary endpoints:

- Numerical Rating Scale (NRS) itch score at Screening, Baseline, Weeks 2, 4, 8, 12, 16, and 18.
- Dermatology Life Quality Index (DLQI) at Screening, Baseline, Weeks 2, 4, 8, 12, 16, and 18.

- AEs; performing physical examinations; collecting vital signs; and collecting laboratory data for hematology, and serum chemistry.

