2.2.3. Exploratory Endpoint(s)

- Skin RNA-seq analysis at Baseline (Week 0) and Week 16.

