4. INVESTIGATIONAL PLAN

4.1. Overall Study Design

This study is an open label pilot study examining the efficacy of apremilast in the treatment of CIP. Ten (10) subjects who meet the eligibility criteria are planned to be enrolled. The total duration of subject participation will be 6 study visits over approximately 16 weeks. All subjects will receive apremilast 30 mg by mouth BID for 16 weeks.

All apremilast subjects will have visits at Screening, Baseline, and Weeks 2, 4, 8, 12, 16, and 18 (follow-up). Adverse events (AEs), medication history, clinical assessments, physical exam, and vital signs will be performed at each visit. Clinical safety laboratories will be performed at screening and Week 16 (EOT). All laboratory assessments will be performed using The Barnes-Jewish Hospital laboratory except for urine pregnancy tests (as applicable). NRS and DLQI scoring will be performed by a research nurse.

Two skin biopsies will be performed at the most pruritic site at Baseline and at Week 16 (adjacent to the initial biopsy site) for histopathological analysis and RNA-seq transcriptional analysis.

After the end-of-treatment visit (Week 16, or early termination), subjects will have follow-up assessments two weeks later (week 18) to monitor for durability of effect (relapse rate), AEs, medication history, vital signs, and clinical assessments.

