9.4.1.2.1 Dermatology Life Quality Index (DLQI)

The DLQI score improvement will be calculated relative to baseline at each visit. The key secondary endpoint is the change from baseline in DLQI at Week 12.

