9.4.3. RNA seq Analysis

Skin gene expression signatures will be performed at baseline and Week 12 to identify RNA signatures associated with treatment response.

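### Section 9.4 puts the primary, key secondary and RNA-seq analyses at Week 12, while the Synopsis, Section 2.2 and the biopsy schedule put them at Week 16; the NRS recall score for the primary test is also not named

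*Combined protocol and SAP*

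**What the plan says.** The endpoint sections and the analysis section give different weeks for all three outcomes.

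- **Primary (NRS itch).** The Synopsis has "Absolute change from Baseline in Numerical Rating Scale (NRS) itch score to week 16" and Section 2.2.1 has "Absolute change in Numerical Rating Scale (NRS) itch score from Baseline to Week 16". Section 9.4.1.1.1 has "The primary endpoint is the change from baseline in NRS at Week 12".
- **Key secondary (DLQI).** Section 2.2.2 has "Absolute change in Dermatology Life Quality Index (DLQI) from Baseline to week 16", and the Synopsis agrees. Section 9.4.1.2.1 has "The key secondary endpoint is the change from baseline in DLQI at Week 12".
- **Exploratory (RNA-seq).** Section 2.2.3 has "Skin RNA-seq analysis at Baseline (Week 0) and Week 16". Section 9.4.3 has "Skin gene expression signatures will be performed at baseline and Week 12". On tissue collection, Section 4.1 says "Two skin biopsies will be performed at the most pruritic site at Baseline and at Week 16", and Table 1 marks the same two visits.

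The primary test is a paired t-test on the NRS score (Synopsis, Sections 9.2 and 9.4.1.2). It compares each subject at two visits that are not named. Section 9.3 sets the significance level at 0.05 without saying whether the test is one- or two-sided.

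Sections 2.2.1, 7.5.1 and 9.4.1.1.1 have the NRS recorded twice at each visit, once for the past 24 hours and once for the past week. None of them makes either score primary.

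**The concern.** A plan that defines its primary endpoint at two different visits has no single primary analysis. One analyst working from Section 2.2 and another working from Section 9.4 would report primary and key secondary results four weeks apart, each with a section to cite. An analyst who followed Section 9.4.3 literally would look for tissue at a visit where none is scheduled.

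The unnamed recall score is a second, smaller gap of the same kind. With two weeks and two scores, up to four analyses could each be presented as the primary one. The study is open label with neither randomization nor blinding (Sections 4.2 and 5.1.2), so the scores are visible as they come in. Fixing the primary analysis in advance is one of the few protections such a design can have. The plan leans on that analysis: Section 9.3 aims for P of 0.05 or lower, and Section 1.7 expects a definite answer on efficacy.

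**Working it through.** **Step 1. The text side by side.**

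| Outcome | Endpoint sections | Section 9.4 | Data collected at |
|---|---|---|---|
| NRS | Week 16 (Synopsis, 2.2.1) | Week 12 (9.4.1.1.1) | both weeks (Table 1) |
| DLQI | Week 16 (Synopsis, 2.2.2) | Week 12 (9.4.1.2.1) | both weeks (Table 1) |
| RNA-seq | Week 16 (Synopsis, 2.2.3) | Week 12 (9.4.3) | Baseline and Week 16 (4.1, Table 1) |

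The weeks differ by 16 − 12 = 4.

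**Step 2. Does anything else settle the week?** The test description does not, because it names no visits. Data availability settles only RNA-seq, since NRS and DLQI exist at both weeks. Section 1.7 gives the reason for the study's length and ties the efficacy judgement to Week 16. The weight of the text therefore favours Week 16, but no sentence overrides Section 9.4.

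**Step 3. Does anything settle the recall score?** No. Section 9.4.1.1.1 mentions an average and an overall score, but it gives no rule for combining the two recalls. The entry threshold of NRS ≥ 7 in Section 3.1 does not say which score it uses either.

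**Step 4. What an open choice could cost.** The plan has no figure of its own to reproduce here. The inputs are:

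- From the documents: n = 10 and level 0.05.
- Assumed: a two-sided test; normally distributed change scores with true mean zero; correlation 0.7 to 0.95 between recall scores and 0.5 to 0.9 between weeks; for a different score at a different week, the product of the two correlations.

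For each candidate, t = mean change ÷ (SD of change ÷ √10). It is rejected when |t| exceeds the 97.5th percentile of the t distribution on 9 degrees of freedom. One test fixed in advance gives 2.5% in the favourable direction and 5% in either.

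Simulation with 400,000 trials per setting gives the chance that at least one of the four candidates is significant:

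| Recall correlation | Week correlation | Favourable | Either direction |
|---|---|---|---|
| 0.7 | 0.5 | 7.7% | 15.4% |
| 0.8 | 0.7 | 6.8% | 13.6% |
| 0.9 | 0.8 | 5.8% | 11.5% |
| 0.9 | 0.9 | 5.2% | 10.3% |
| 0.95 | 0.9 | 4.7% | 9.5% |

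With only one choice left open there are two candidates:

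| Correlation | Either direction |
|---|---|
| 0.5 | 9.2% |
| 0.7 | 8.5% |
| 0.8 | 8.1% |
| 0.9 | 7.2% |
| 0.95 | 6.6% |

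Two positively correlated tests almost never reject in opposite directions, so the favourable rate is about half of these:

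- Week choice alone (0.5 to 0.9): 9.2 ÷ 2 to 7.2 ÷ 2, about 4.6% to 3.6%.
- Recall choice alone (0.7 to 0.95): 8.5 ÷ 2 to 6.6 ÷ 2, about 4.2% to 3.3%.

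For reference, independent tests would give 1 − 0.95² = 9.75% for two and 1 − 0.95⁴ = 18.5% for four, in either direction.

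**The case against.** The strongest reply is that Week 12 in Section 9.4 is a drafting slip and any reader can see it. The Synopsis, Section 2.2, the rationale in Section 1.7 and the biopsy schedule all point to Week 16, and Section 9.4.3 cannot be carried out as written for a subject who completes treatment. This is probably right, and it is why the correction should run towards Week 16. It does not make the text correct. All three week numbers in Section 9.4, the section an analyst works from, are at odds with the endpoint definitions, and for NRS and DLQI the Week 12 analysis can be run without anything looking amiss.

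The second reply is that the error rates are hypothetical. This stands. No passage plans four tests or a choice among them after seeing results. The correlations are not in the documents, and normal change scores are a rough model for an 11-point scale entered at 7 or above. If the week is read as 16, only the recall choice is left. The simulation also assumes no average change, whereas an uncontrolled study that selects high scores can show a fall without any drug effect. The rates illustrate the point and do not carry it.

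The third reply is that the items differ in weight, which is also fair. The week is a contradiction. The recall score is a secondary omission. The score behind the entry criterion and the unclear averaging phrase are minor details.

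An early-termination visit could yield a biopsy before Week 16, because end-of-treatment procedures are then to be completed (Sections 6.4 and 6.7). That does not supply Week 12 tissue from completers.

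**Conclusion.** The concern holds. Section 9.4 contradicts the plan's own definitions of the primary, key secondary and exploratory endpoints by four weeks, and for RNA-seq it points to a visit with no scheduled biopsy. This rests on the text alone. The plan also fails to say which of two NRS scores enters the primary test, and nothing in the documents favours either one.

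If the choice were made after seeing the data, the favourable false-positive rate would be about 4.7% to 7.7% for all four candidates, or about 3.3% to 4.2% if only the recall score were open, against 2.5%. These ranges depend on the assumed correlations, a two-sided test, normal change scores and a choice that no passage plans. The point must be fixed before analysis because it concerns what the primary result is.

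**What to change.** 1. Change Week 12 to Week 16 in Sections 9.4.1.1.1, 9.4.1.2.1 and 9.4.3, and name Baseline and Week 16 as the two visits in the paired t-test (Section 9.4.1.2, with matching words in Section 9.2 and the Synopsis). Week 12 NRS and DLQI stay as the secondary time points already listed in Section 2.2.2.
2. Before analysis, have the investigator designate one recall score, 24-hour or one-week, for the primary NRS change and report the other as supportive. Either is defensible; what matters is that one is named.
3. In the same amendment, say which score the NRS ≥ 7 entry criterion refers to, and clarify or delete the phrase about an overall average in Section 9.4.1.1.1.

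The cost is a short wording amendment with the sponsor and IRB/IEC approval that Section 10.1 requires. It needs no new visits, data or subjects. With one week and one score fixed, there is a single primary test at the stated 0.05 level. This removes the ambiguity only: it does not turn P < 0.05 in an uncontrolled open-label study into evidence of a drug effect.
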